### *After end of treatment*

To ensure the most conservative approach for the time-to-event variables (i.e., DR, PFS and OS), which can be affected by missing values, the following rules will be implemented: if the day of a date is unknown then the imputed day will be the 1st; if the month is also unknown, then the imputed date will be the 1st of July. This assumption will be valid if the imputed date occurs later than the last drug administration date; otherwise the imputed date will be the date of the last drug administration plus the predefined cycle length (i.e., 21 days if PM01183), except if the patient dies before, in which case the date of death minus 1 will be used.

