#### Secondary endpoint

The following time-related parameters would be analyzed according to available follow-up data:

**Duration of response (DR)** is defined as time from first observation of response to the date of disease progression, recurrence or death. Other causes will be censored. Although the responses have to be confirmed according to RECIST v1.1 criteria, the first documentation, not the confirmation, will be taken into account to calculate DR. Patients who progress or die will be considered to have had an event, except if this event occurs after the start of subsequent antitumor therapy, in which case the patient will be censored at the time of last disease assessment prior to or on the first day of the first subsequent antitumor therapy.

**Clinical benefit rate** is calculated as the number of patients who have had CR or PR or SD  $\geq 3$  months as overall best response according to the RECIST v1.1 criteria, divided by the number of patients in the “All Evaluable Patients” analysis set.

**Progression-free survival (PFS)** is defined as the time from start of treatment to the date of documented progressive disease (PD) by RECIST v1.1 criteria or death (regardless of the cause of death), whichever comes first. Patients who progress or die will be considered to have had an event, except if this event occurs after the start of subsequent antitumor therapy, in which case the patient will be censored at the time of last disease assessment prior to or on the first day of the first subsequent antitumor therapy. If the patient is lost for the assessment of progression during the follow-up period, or has more than one missing follow-up between the date of last tumor assessment and the date of progression, death or further antitumor therapy, the PFS will be censored at the date of last valid disease assessment before the missing evaluations.

**Overall survival (OS)** is defined as the time from the date of start of treatment to the date of death or last contact. **1 year overall survival (1y-OS)** is defined as the Kaplan-Meier estimate of the probability of patients alive after 12 months from the date of start of treatment.

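### The post-treatment date rule in SAP 8.8 is not conservative for PFS and DR, and it allows progression and death dates that the patient's own record contradicts

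*SAP*

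**What the plan says.** SAP 8.8 divides incomplete dates into those before registration, those between treatment start and end of treatment, and those after end of treatment. The last group carries the stated aim: "To ensure the most conservative approach for the time-to-event variables". A missing day becomes the 1st of the month, and a missing month as well gives 1 July. The lower bound is the last infusion: "This assumption will be valid if the imputed date occurs later than the last drug administration date". If that fails, "otherwise the imputed date will be the date of the last drug administration plus the predefined cycle length" (21 days), "except if the patient dies before, in which case the date of death minus 1 will be used". Progression, death and new-therapy dates are not distinguished.

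SAP 6.1 counts progression or death as a PFS or DR event "except if this event occurs after the start of subsequent antitumor therapy". In that case the patient is censored at the last assessment on or before the first day of the new therapy. OS runs to death or last contact. Protocol 6.8 follows survival every six months after progression or new therapy, by telephone if need be, so the last contact can fall long after the last dose. SAP 8.10 only tabulates missing values. Neither document checks the order of imputed dates.

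**The concern.** Setting an unknown date early is conservative when the date is an event, because it shortens the time. It is the reverse when the date is the trigger that removes events. For a new-therapy start, an earlier date can only push progressions into the censored group. Losing events raises the Kaplan-Meier curve, and with no control arm nothing offsets the rise.

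Separately, with only the last dose as a floor, the rule followed exactly can date a death before the patient was last known alive, or a progression before a clean scan. Correcting such records at analysis would then be an unplanned departure from the SAP in an open-label trial.

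**Working it through.** The plan states no figure on this point, so there is none to reproduce. I applied SAP 8.8 and then SAP 6.1 literally to example dates (all 2016).

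| Known facts | Imputed | Result |
|---|---|---|
| A. Last dose 20 Apr; progression 12 May; therapy in May, day missing (true 26 May) | therapy 1 May | progression follows therapy: event becomes censored |
| B. Last dose 10 Mar; progression in March, day missing (true 18 Mar); therapy 25 Mar | 1 Mar fails the bound; 10 Mar + 21 = 31 Mar | event becomes censored |
| C. Last dose 10 Feb; progression month missing (true 5 Apr); therapy 2 May | progression 1 Jul | event becomes censored |
| D. Last dose 10 Jan; last contact 20 May; death in May, day missing | death 1 May | 19 days before last known alive |
| E. Last dose 10 Jan; last contact 20 Oct; death month missing | death 1 Jul | 111 days before last known alive |
| F. Last dose 10 Jan; death month missing (true 15 Feb) | death 1 Jul | OS lengthened by 137 days |
| G. Last dose 20 May; death in May, day missing | 20 May + 21 = 10 Jun | outside the recorded month |

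The exception for a patient who dies first needs a known death date, so it cannot repair D to G.

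**Share of type A cases, given a missing therapy day.** Ignoring the last-dose bound, a progression g days before therapy is lost when the 1st of the therapy month precedes it. With a mean month of 366/12 = 30.5 days, the share is (30.5 − g − 1)/30.5:

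- g = 7: 22.5/30.5 = 74%
- g = 14: 15.5/30.5 = 51%
- g = 21: 8.5/30.5 = 28%
- g = 28: 1.5/30.5 = 5%

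The same formula applies to type D. With the last contact 3, 7, 14 or 21 days before death and only the day missing, the imputed death precedes that contact in 87%, 74%, 51% or 28% of cases.

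**Effect on six-month PFS, by simulation.** From Protocol 7.1: scans every 6 weeks to Cycle 6 (6 × 21 = 126 days), then every 9 weeks, so days 42, 84, 126, 189 and on. Assumed, because the documents do not give them: exponential PFS with median 120 days; last infusion 14 to 21 days before progression; every progressor starts new therapy; uniform gap to new therapy; 10% of therapy starts lack a day. The last-dose bound is applied, and affected patients are censored at the preceding scan.

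| Gap, progression to therapy | Same month | Lost if day missing | Lost at 10% partial | Six-month PFS |
|---|---|---|---|---|
| 14–42 days | 16% | 14% | 1.4% | 48.3% → 48.7% |
| 7–28 days | 42% | 36% | 3.6% | 48.3% → 49.5% |
| 1–14 days | 75% | 53% | 5.3–5.4% | 48.3% → 50.1% |

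The 48.3% baseline comes from the scan grid: 2^(−126/120) = 0.483, since the next scan, day 189, falls just after six months. The underlying curve at 183 days is 2^(−183/120) = 35%.

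If only half of progressors start therapy in the window, the losses are 0.7%, 1.8% and 2.7%. The loss scales with the partial-date rate: at 30% it would be 3 × 1.4% = about 4% up to 3 × 5.3% = about 16%.

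**Which window applies.** SAP 8.4 and Protocol 6.2 put end of treatment at 30 days after the last dose, or at the new therapy if sooner. Some of these dates may therefore fall under the rule for the period between treatment start and end of treatment. That rule also imputes day 1, with the weaker floor of treatment start. The shares lost given a missing day are then 14%, 39% and 72% for the three gaps, so the problem remains.

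**The case against.** The strongest reply is that this is small and conditional. The documents give no frequency of partial dates and no distribution of the time to next therapy. A therapy start within 30 days of the last dose defines end of treatment and stops routine adverse-event collection, so sites have reason to record it fully. Scans are six or more weeks apart and survival contacts six-monthly after progression, so a contact or clean scan will seldom share a month with the event. The trial is exploratory, and PFS, DR and OS carry no decision threshold. At n = 53 a rate of 48% has a 95% half-width of 1.96 × √(0.48 × 0.52/53) = 13.5 points, against a shift of 0.4 to 2. All of this stands as a limit on size. None of it stops the rule from giving a wrong event status when a partial date occurs.

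Three stronger readings are not supported:

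- A reader might infer that impossible death dates flatter OS. Cases D and E shorten it, which is conservative in direction though contradicted by the record. Only cases such as F and G lengthen it.
- A reader might infer that every partial date loses an event. If progression and therapy both lack a day in the same month and the 1st is after the last dose, both become the 1st and the event is kept. A progression lacking only its day, in a month after the last-dose month, moves earlier and remains an event unless therapy is placed before it.
- A reader might infer a material bias in reported PFS. Without the frequency of partial dates, that cannot be said.

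**Conclusion.** The point holds as a defect in the rule as written. SAP 8.8 with SAP 6.1 can turn a fully documented progression into a censored record, contrary to the stated aim. It can also place imputed deaths and progressions before dates on which the patient was known to be alive or progression-free. The 1 July value is close to a mid-year convention and can err in either direction. Nothing else in the SAP or protocol prevents these results.

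The likely size is modest: with 10% partial therapy starts and all progressors treated, about 1.4% to 5.4% of progressions are lost and six-month PFS rises by about 0.4 to 2 points, or roughly half that if half of progressors start therapy in the window. These figures rest on assumed inputs. The primary endpoint, ORR, is not touched. The change is worth making because it is cheap and removes a contradiction, not because the trial's main conclusion depends on it.

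**What to change.** Amend SAP 8.8, in both the during-treatment and the after-treatment rules wherever they feed DR, PFS or OS:

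- Impute a partial subsequent-therapy start as the latest of the 1st of the month, the existing last-dose bound, and the day after any progression documented in that month.
- Bound an imputed death below by the day after last known alive, and an imputed progression by the day after the last progression-free assessment.
- Keep every imputed date within the recorded month or year.
- Otherwise, for events, use the earliest date consistent with the known facts, or remove the claim that the approach is the most conservative.

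The cost is a few lines of text and programming. There is one downside: a patient whose new therapy truly began before progression in the same month, whom SAP 6.1 would censor, is kept as an event. That error is in the conservative direction and should be acknowledged in the text.

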### **8.9 Subgroup Analysis**

The analysis will be done by Cohort and additionally, if clinically appropriate, the Cohorts might be pooled into one, whenever differences between Cohorts are considered not relevant. In such case, the point estimates and their 95% CIs will be also reassessed in order to obtain more accurate calculations.

Efficacy subgroup analysis will be performed in Cohort A according to prior treatment with platinum (Yes vs. No), BRCA status (BRCA1 vs. BRCA2), hormonal status (Triple negative vs. HR+), number of advanced chemotherapy lines , prior PARPi (Yes vs. No)and starting dose (7 mg FD vs. 3.5 mg/m^2).

Additional efficacy subgroup analysis will be performed in Cohorts A+A1 according to prior PARPi (Yes vs. No). Safety subgroup analysis will be performed according to starting dose (7 mg FD vs. 3.5 mg/m^2), these analysis include laboratory abnormalities and adverse events.

If clinically relevant, other subgroup analysis may be performed in order to explore the activity of PM01183 in specific breast cancer subpopulations.

No differentiation by center is planned.

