5.2. ADMINISTRATION OF STUDY MEDICATIONS

5.2.1. Route of administration, starting dose, and schedule

Patients included under protocol versions 1.0 and 2.0 will receive PM01183 i.v. as a one-hour infusion on Day 1 q3wk at a starting dose of 7.0 mg FD (three weeks = one treatment cycle).

Patients included from protocol version 3.0 onward (after implementation of amendment no. 2) will receive PM01183 i.v. as a one-hour infusion on Day 1 q3wk at a starting dose of 3.5 mg/m² (three weeks = one treatment cycle). Dose will be capped at BSA of 2.0 m² (i.e., dose will not exceed 7 mg). BSA will be calculated according to standard practice at each center.

PM01183 will be administered over a minimum total volume of 100 ml of solution for infusion (either on 5% glucose or 0.9% sodium chloride) through a central catheter or over a minimum total volume of 250 ml if through a peripheral line, always over one hour at a fixed infusion rate.

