#### 11.1.12 Baseline and demographic characteristic comparisons

Table 11.1.12.1 Baseline and demographic characteristic comparisons by cohorts

		N	Cohort A	Cohort A1	Cohort B	p-value*
Age	Median (range)	X	X.X (XX-XX)	X.X (XX-XX)	X.X (XX-XX)	X.XXXX
PS (ECOG)	0	X	X ( XX.X %)	X ( XX.X %)	X ( XX.X %)	X.XXXX
	1	.	X ( XX.X %)	X ( XX.X %)	X ( XX.X %)	
BSA	Median (range)					
BRCA mutation	1					
	2					
Receptor status	Triple negative					
	HR+ / HER2 -					
	HER2 +					
Liver metastases	Yes					
	No					
CNS metastases	Yes					
	No					
Sites involvement	<3 sites					
	≥ 3 sites					
Advanced lines	Median (range)					
Advanced CT lines	Median (range)					
Prior Platinum	Yes					
	No					
Prior Anthracyclines	Yes					

		N	Cohort A	Cohort A1	Cohort B	p-value*
	No					
Prior Taxanes	Yes					
	No					
Prior Capecitabine	Yes					
	No					
Prior PARP Inhibitor	Yes					
	No					

\*Fisher's exact test (categorical variables);Mann-Whitney-Wilcoxon (continuous variables)

Table 11.1.12.2 Baseline and demographic characteristic comparisons: Platinum Yes/No in Cohort A

		N	Prior platinum Yes	Prior platinum No	p-value*
Age	Median (range)	X	X.X (XX-XX)	X.X (XX-XX)	X.XXXX
PS (ECOG)	0	X	X ( XX.X %)	X ( XX.X %)	X.XXXX
	1	.	X ( XX.X %)	X ( XX.X %)	
...	...				

\*Fisher's exact test (categorical variables);Mann-Whitney-Wilcoxon (continuous variables). For the complete list of covarites, see table 11.1.12.1

Table 11.1.12.3 Baseline and demographic characteristic comparisons: BRCA 1 vs 2 in Cohort A

		N	BRCA 1	BRCA 2	p-value*
Age	Median (range)	X	X.X (XX-XX)	X.X (XX-XX)	X.XXXX
PS (ECOG)	0	X	X ( XX.X %)	X ( XX.X %)	X.XXXX
	1	.	X ( XX.X %)	X ( XX.X %)	
...	...				

\*Fisher's exact test (categorical variables);Mann-Whitney-Wilcoxon (continuous variables). For the complete list of covarites, see table 11.1.12.1

Table 11.1.12.4 Baseline and demographic characteristic comparisons: Prior PARPi Yes/No in Cohorts A+A1

		N	Prior PARPi Yes	Prior PARPi No	p-value*
Age	Median (range)	X	X.X (XX-XX)	X.X (XX-XX)	X.XXXX
PS (ECOG)	0	X	X ( XX.X %)	X ( XX.X %)	X.XXXX
	1	.	X ( XX.X %)	X ( XX.X %)	
...	...				

\*Fisher's exact test (categorical variables);Mann-Whitney-Wilcoxon (continuous variables). For the complete list of covarites, see table 11.1.12.1

Table 11.1.12.5 Baseline and demographic characteristic comparisons: Initial dose 7 mg FD vs 3.5 mg/m^2 in Cohort A

		N	7 mg FD	3.5 mg/m 	p-value*
Age	Median (range)	X	X.X (XX-XX)	X.X (XX-XX)	X.XXXX

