### **11.3 Efficacy Analysis**

Efficacy analysis will be carried out on the “All Evaluable Patients” population.

Subgroup analysis will be performed in Cohort A according to prior treatment with platinum, BRCA status (BRCA1 vs. BRCA2), hormonal status (Triple negative vs. HR+), number of advanced chemotherapy lines, prior PARPi (Yes vs. No) and starting dose (7 mg FD vs. 3.5 mg/m^2).

Subgroup analysis will be performed in Cohorts A+A1 according to prior PARPi (Yes vs. No).

The tables included in each subgroup analysis are the following:

Table 11.3.1.1 Response rate

Table 11.3.1.2 Overall response rate

Table 11.3.2.1 Duration of response

Table 11.3.2.2 Progression-free survival (PFS)

Table 11.3.2.3 Overall survival (OS)

The tables will be annotated by adding a letter as suffix:

- BRCA status: a
- Prior platinum: b
- Hormonal status: c
- Advanced chemotherapy lines: d
- Starting dose: e
- Prior PARPi (Cohort A): f
- Prior PARPi (Cohorts A+A1): g

If any other disease characteristic is sufficiently represented and clinically relevant, subgroup analysis may be performed, and their corresponding tables will also be annotated by adding a letter to the table’s name.

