### **12.2 Adverse Events**

#### **12.2.1 Adverse Events**

As far as all the toxicities are concerned, the NCI-CTC grade will be used wherever an NCI-CTC grading exists. Otherwise, the severity will be noted. As a convention, the term «Grade» will always be used. Toxicities will be described according to the worst NCI-CTC grade or, for toxicities which do not form the subject of NCI-CTC classification, according to the worst severity.

Adverse events will be described in this section; treatment-related events (stated as related to the study drug or of unknown relationship) will be tabulated.

Type of toxicity and worst grade or severity by cycle and by patient will be summarized according to the Preferred Term coded with MedDRA. Tables will be organized per category of events using System Organ Class of MedDRA.

Subgroup analysis will be performed according to starting dose (7 mg FD vs. 3.5 mg/m^2) and Cohort.

The groups will include:

- Patient treated at 7 mg FD Cohort B
- Patient treated at 7 mg FD Cohort A
- Patient treated at 7 mg FD any Cohort
- Patient treated at 3.5 mg/m^2 Cohort A
- Patient treated at 3.5 mg/m^2 Cohort A1
- Patient treated at 3.5 mg/m^2 any Cohort

The tables will be annotated by adding a letter as suffix.

The tables included in the subgroup analysis are the following:

Table 12.2.2.2 Treatment related AEs. Worst grade by patient

Table 12.2.2.3 Treatment related AEs. Worst grade by cycle

Table 12.2.2.4 Adverse events regardless of relationship. Worst grade by patient

Table 12.2.2.5 Adverse events regardless of relationship. Worst grade by cycle

If clinically relevant the outputs could be split by initial dose or any other characteristic.

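### The exploratory prior-PARPi comparison in Cohorts A+A1 is partly confounded with starting dose, and its tables as specified do not separate the two

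*SAP*

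**What the plan says.** SAP 8.9 plans the comparison: "Additional efficacy subgroup analysis will be performed in Cohorts A+A1 according to prior PARPi (Yes vs. No". SAP 11.3 repeats it and gives it its own table suffix, "Prior PARPi (Cohorts A+A1): g". The suffix covers five tables: response rate, overall response rate, duration of response, PFS and OS. Neither section restricts, stratifies or adjusts this comparison by starting dose.

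Starting dose depends on when a patient entered. Protocol 5.2.1 assigns a 7.0 mg flat dose to one group ("Patients included under protocol versions 1.0 and 2.0 will receive PM01183 i.v. as a one-hour infusion") and 3.5 mg/m2 to the other ("Patients included from protocol version 3.0 onward (after implementation of amendment no. 2"). SAP 14.1 dates amendment 2 to October 2014.

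SAP 12.2.1 and 12.4 list the dose-by-cohort groups for the safety tables. Cohort A appears at 7 mg flat dose and at 3.5 mg/m2. For A1 the only entry is "Patient treated at 3.5 mg/m 2 Cohort A1". Cohort B appears only at 7 mg flat dose.

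The balance table for the comparison is Table 11.1.12.4, "Baseline and demographic characteristic comparisons: Prior PARPi Yes/No in Cohorts A+A1". It takes its rows from Table 11.1.12.1, which has BSA but no starting dose. SAP 6.2.2 names both initial dose and prior PARPi as candidate covariates for exploratory multivariate models.

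**The concern.** Every A1 patient has had a prior PARP inhibitor (SAP section 2), so pooling A1 with A adds patients to the Yes group only, and by the SAP's lists all of them started at 3.5 mg/m2. The No group comes entirely from Cohort A, which mixes the two regimens. The two groups can therefore differ in starting dose and enrolment period as well as in PARPi history.

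Suffix g is the only planned pooled analysis of whether activity differs after a PARP inhibitor. If the regimens differ in efficacy, its tables could suggest a loss of activity that belongs to the regimen, or conceal one that is real. The SAP itself treats starting dose as worth examining for efficacy: it plans a starting-dose subgroup in Cohort A (suffix e).

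**Working it through.** **The plan's own figure.** The documents give no figure for the A+A1 comparison. The nearest is the A1 criterion in SAP 5.1, that at least 4 responders of 20 puts the exact 95% lower limit above 5%. The exact interval for 4/20 is 5.7% to 43.7%, and 3/20 gives a lower limit of 3.2%. The statement is right. It is not comparative, so the present point does not touch it.

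**Who is in each group.**

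| Group | Source | Starting dose in the SAP lists |
|---|---|---|
| PARPi Yes | A1 (planned 20) plus any prior-PARPi patients in A | A1: 3.5 mg/m2 only; A: both |
| PARPi No | A only (at least 53 in the cohort) | both |

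The confounding is partial. Cohort A has 3.5 mg/m2 patients, and SAP 8.9 also plans a prior-PARPi split inside Cohort A (suffix f), which implies some prior-PARPi patients there. How many is not stated. Protocol 4.1 places the prior-PARPi inclusion criterion under Cohort A, while the synopsis places it under A1. These passages must be reconciled, because they bear on who falls in each group.

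**Do other outputs already deal with it?**
- Table 11.1.12.4 cannot show the imbalance, having no dose row.
- Table 11.1.12.5 compares the dose groups on a list that includes prior PARP inhibitor, but only in Cohort A.
- The 6.2.2 models are run if judged appropriate. Covariates are screened at univariate p < 0.10 and then selected stepwise at 0.05, so neither dose nor prior PARPi need be retained.

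**Possible size (assumptions, not document figures).** With no true PARPi effect and a regimen difference g in response rate:

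gap (No minus Yes) = g × (flat-dose share in No − flat-dose share in Yes)

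Assume the Yes group is all at 3.5 mg/m2 and the No group is 53 PARPi-naive Cohort A patients, n7 of them on flat dose. The gap is then g × n7/53, whatever the response rate at 3.5 mg/m2:

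| n7 | g = 10 points | g = 15 points | g = 20 points |
|---|---|---|---|
| 20 | 3.8 | 5.7 | 7.5 |
| 30 | 5.7 | 8.5 | 11.3 |
| 40 | 7.5 | 11.3 | 15.1 |

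If flat dose were the less active regimen, the signs reverse.

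**Prior-PARPi patients in Cohort A.** Take g = 20 points and half of the 53 on flat dose. With no prior-PARPi patients in A the gap is 0.20 × 0.50 = 10.0 points. With ten who share the cohort's dose mix, the flat-dose shares are 21.5/43 = 0.50 in No and 5/30 = 0.167 in Yes, so the gap falls to 6.7 points. If all ten had started at 3.5 mg/m2 instead, the shares are 26.5/43 = 0.616 and 0, and the gap is 12.3 points.

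**Chance of a nominally significant difference.** This takes 20 against 53, no PARPi effect, and a two-sided Fisher test at 0.05.

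| Flat-dose patients among the 53 | ORR 40% flat vs 30% | ORR 40% flat vs 20% |
|---|---|---|
| 0 | 3.6% | 3.1% |
| 13 | 3.6% | 4.0% |
| 27 | 4.4% | 9.4% |
| 40 | 5.8% | 17.6% |

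The 10-point regimen difference barely moves the error rate. The 20-point difference does, once most of Cohort A is on flat dose.

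**The case against.** The strongest reply is that these are descriptive tables in a trial labelled exploratory. The suffix-g outputs show counts, proportions with intervals and Kaplan-Meier summaries, with no p-value, and tests under 6.2.2 are optional. Dose is visible nearby: suffix e gives the same five tables by starting dose in Cohort A, and Listing 11.3.2.5 shows the initial dose of each patient with clinical benefit. All of this stands and limits the weight of the point. None of it is tied to suffix g, however, and none extends the dose comparison to A1, where the imbalance arises.

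A second reply is that the assumed regimen effect has no source. Under the cap ("Dose will be capped at BSA of 2.0 m² (i.e., dose will not exceed 7 mg") a patient with an assumed BSA of 1.75 m2 starts at 3.5 × 1.75 = 6.1 mg, 12.5% below 7 mg, and Protocol 1.2.1.2 reports clearance unrelated to BSA. A 20-point effect equals the whole distance between Cohort A's null and alternative rates. This also stands: the illustration shows what could happen, not what is expected.

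A third reply concerns precision. With 40 of 53 on flat dose, restriction leaves 13 PARPi-naive patients against 20. At a 30% response rate the approximate 95% half-width of the difference goes from 1.96√[0.21(1/53 + 1/20)] = 24 points to 1.96√[0.21(1/13 + 1/20)] = 32 points. That is a fair cost. It is a reason to keep the pooled table alongside, not to rely on it alone.

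**Conclusion.** The point holds as a limited one. As specified, the suffix-g tables mix prior PARPi with starting dose and enrolment period, and the planned balance table would not reveal it. Any resulting bias is of unknown size and direction. The 4 to 15 point range is an illustration that assumes no PARPi effect, an all-3.5 mg/m2 Yes group, a PARPi-naive Cohort A with 20 to 40 of 53 on flat dose, and a 10 to 20 point regimen difference. It shrinks if prior-PARPi patients in Cohort A share that cohort's dose mix.

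A reader might infer that the trial cannot separate a PARPi effect from a regimen effect, or that a regimen difference would inevitably be reported as PARPi resistance. The documents do not support either reading. The regimens overlap within Cohort A, so a like-for-like comparison at 3.5 mg/m2 is possible, and the tables carry no planned conclusion. That A1 received one regimen is itself an inference from the SAP's group lists; no section says so outright. The primary response-rate tests and the A1 criterion of at least 4/20 do not depend on this comparison.

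**What to change.** In SAP 8.9 and 11.3, report the suffix-g tables also by starting dose: either within patients from A and A1 who started at 3.5 mg/m2, or stratified by starting dose. Base any statement about a prior-PARPi effect on that version, and show the pooled unstratified table beside it. Add a starting-dose row to the Table 11.1.12.1 list so that Table 11.1.12.4 displays the imbalance.

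Under the assumptions above, restriction or stratification makes the dose-induced gap zero in expectation. It does not remove confounding by other unrandomised differences, and the report should say so.

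The cost is SAP wording and re-running existing tables on a subset or with one stratum variable. The price is fewer PARPi-naive patients and wider intervals. Treatment and trial conduct do not change.
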